#### Visit 5–6

The day after the completion of each arm (control and Carry Life® UF), the subject will visit the clinic for data collection according to Table 1. The Carry Life® UF end-of-arm visit will be performed the day after the last Carry Life® UF treatment. The end-of-arm visits should be planned to be performed on the same day of the week, e.g., for a subject who started the study arms on a Wednesday, the last treatment of the arm will be on a Monday and the end-of-arm visits will be on a Tuesday. Starting two days before the end-of-arm visits, a 24-hour urine sample will be collected, unless the subject is anuric (< 100 ml urine volume/24 hours), and analyzed according to Table 1. Visit 6 will be the completion of the study for the subject. Upon completion of the study, subjects who had their PD prescription adjusted to enable entry into the study have the option of returning to their previous prescription.

Subjects who prematurely end the study will undergo an end-of-study visit.

#### 6.2.6 Description of measures to minimize or avoid bias

The Sponsor will avoid improper influence on any parties participating in, or contributing to, the clinical investigation or the induction thereof. The selection and treatment of participants and evaluation of clinical investigation data are potential sources of bias. Methods that are incorporated within the clinical investigation design to minimize potential bias include, but are not limited to, screening participants to confirm eligibility with defined inclusion/exclusion criteria prior to enrolment; maintaining a log of all participants screened and enrolled; collecting demographics, medical history, and medications at baseline to later assess possible characteristics that may influence endpoints; standardizing data collection requirements and clinical investigation procedures; using standardized training materials for all study personnel; and by conducting regular monitoring visits to verify adherence to the CIP and source data.

As the clinical investigation involves the use of a medical device it is not possible to blind the investigational staff or the patients. Randomizing the order of the study arms in this cross-over study will minimize the risk that a general disease progress affects the outcome.

The UF volume result may be biased if the peritoneal drain is performed in different subject positions during the drain. During the efficacy evaluation days the subject will be instructed to perform the study drains in the sitting position.

The UF volume is determined by the length of the treatment. Both the control dwell and the Carry Life® UF dwells during the efficacy evaluation days therefore should be of similar duration. In a standard CAPD dwell, maximum UF occurs after around 2 hours after which it slowly decreases as there will be a net fluid absorption when the osmotic pressure gets too low. The treatment time for both the control and the Carry Life® UF treatment is defined as the time between the end of peritoneal fill and the start of the peritoneal drain. For the control dwell, the subject will be instructed to start the peritoneal drain 5 hours after the end of the peritoneal fill. Both start time and end time will be recorded. For the Carry Life® UF There will be a short delay between the end of fill and start of treatment of the Carry Life® UF device for connection and priming of the system. The Carry Life® UF treatment automatically stops 5 hours 0/+15 min after the start of treatment. The Carry Life® UF treatment therefore is expected to be up to 20 min longer than the control dwell. This bias is in favor of the control dwell as a longer control dwell after a 5-hour dwell time would result in an equal or lower UF volume.

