## 2.6 GENERAL DESCRIPTION OF THE CARRY LIFE® UF SYSTEM

In CAPD, the glucose concentration of the PD fluid is reduced as the glucose is absorbed across the peritoneal membrane, resulting in a reduced UF rate or even fluid re-absorption by the end of the dwell.

The Carry Life® UF is a novel system that performs peritoneal dialysis with the method of steady concentration PD. Throughout the 5-hour Carry Life® UF treatment glucose is administered to the dialysate in the patient's peritoneal cavity to compensate for glucose absorption. By doing this the glucose concentration in the dialysate is sustained and the peritoneal UF is maintained throughout the treatment. Treatment with Carry Life® UF will result in an increased UF volume compared to a 2.27% CAPD dwell. Furthermore, removal of low molecular weight solutes may occur during the treatment as these will follow with the fluid, i.e., with convective solute transport.

The Carry Life® UF treatment starts with an initial fill of the peritoneal cavity with a 1.5 L or 2 L 1.36% glucose PD solution. Following dressing of the Carry Life® UF cycler with the line set and connecting the 50% glucose solution in accordance with the instructions in the IFU, the device is connected to the patient and priming of the line set is performed using a small amount of the IP fluid from the initial fill which is emptied into the drainage bag.

During the treatment a small volume of IP fluid is transferred back and forth between the peritoneal cavity and the device. Glucose is mixed and diluted in the IP fluid, which is transferred into a reservoir bag (pressure chamber bag) inside the pressure chamber of the device. The addition of glucose occurs in 13.5-minute cycles during which approximately 70 ml of IP fluid is transferred at 30 second

intervals to and from the device. When the glucose volume to be dosed each cycle has been administered, the glucose pump remains stopped until the next cycle begins. The device automatically drains approximately 180 ml of dialysate every hour into a drainage bag resulting in approximately 900 ml UF being drained during the 5-hour treatment.

The device can administer two different glucose doses: 11 g and 15 g glucose per hour.

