### 5.1 OBJECTIVES

#### 5.1.1 Primary objective

The primary objective of the clinical investigation is:

- To demonstrate that a 5-hour Carry Life® UF treatment at home results in an increased UF volume compared to a 5-hour 2.27% glucose CAPD dwell in adult CAPD patients.

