### 5.2 HYPOTHESES TO BE ACCEPTED OR REJECTED BY STATISTICAL DATA FROM THE CLINICAL INVESTIGATION

#### Primary endpoint hypothesis

The UF volume achieved with the Carry Life® UF system is superior compared to the UF volume achieved with CAPD using a 2.27% glucose PD solution during a 5-hour treatment.

Hypothesis:

:  $H_0: \mu_d \leq \delta$   
H1:  $\mu_d > \delta$

Where  $\mu_d$  is the average paired difference in UF volume and  $\delta$  is the superiority margin of 250 ml.

Where  $H_0$  is rejected if the following is true:

$$\frac{(\hat{\epsilon} - \delta)}{\frac{\hat{\sigma}_m}{\sqrt{2n}}} < t_{\alpha, 2n-2}$$

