## 6.2.7 Endpoints

### 6.2.7.1 Primary endpoint

The primary endpoint has been defined to address the primary objective; to demonstrate that Carry Life® treatment at home results in an increased UF volume compared to a 2.27% glucose CAPD dwell.

Primary endpoint:

UF volume during 5-hour treatments at home (Carry Life® UF treatment vs. a 2.27% glucose CAPD dwell).

Rationale for the primary endpoint:

Carry Life® UF has been developed to address inadequate fluid management in PD patients which has been associated with increased morbidity, mortality, and technique failure.

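### Section 6.2.6 says the longer device treatment favours the control; that depends on the reference duration, and against the stated 5-hour endpoint the overrun is expected to favour the device.

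*Protocol*

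**What the plan says.** Section 6.2.6 of the protocol starts from the premise that "The UF volume is determined by the length of the treatment" and asks for similar durations in the two arms. It measures treatment time in both arms from the end of the fill to the start of the drain.

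- **Control:** the subject is told to start draining 5 hours after the end of the fill.
- **Device:** there is a short delay for connection and priming, and then "The Carry Life® UF treatment automatically stops 5 hours 0/+15 min after the start of treatment".

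The section concludes that "The Carry Life® UF treatment therefore is expected to be up to 20 min longer than the control dwell". It classes the mismatch as conservative, on the ground that more time would not raise control UF: "This bias is in favor of the control dwell as a longer control dwell after a 5-hour dwell time would result".

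The target of the trial is stated in terms of 5 hours:

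- The primary objective (5.1.1) is that a 5-hour device treatment "results in an increased UF volume compared to a 5-hour 2.27% glucose CAPD dwell in adult CAPD patients".
- The primary hypothesis (5.2) refers to the volume "achieved with CAPD using a 2.27% glucose PD solution during a 5-hour treatment".
- The endpoint (6.2.7.1) is "UF volume during 5-hour treatments at home (Carry Life® UF treatment vs. a 2.27% glucose CAPD dwell").

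Section 6.2.5 says that the control dwell has the same duration as the device treatment. Section 2.6 says of the device that "the glucose concentration in the dialysate is sustained and the peritoneal UF is maintained throughout the treatment".

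**The concern.** The argument in 6.2.6 looks only at the control curve. It asks what the control would do if it were extended to the device's duration, and answers that it would gain nothing or lose a little. It does not ask what the device gains in its extra minutes. Against a 5-hour endpoint that second question decides the direction, because the control is already at 5 hours and the device is the arm that departs from it.

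UF volume is the primary endpoint and is tested against a fixed margin of 250 ml. A reader of 6.2.6 is told that the time mismatch can only make the test harder to pass. Against the trial's own endpoint it is expected to make the test slightly easier.

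**Working it through.** **The plan's own figure.** The 20 minutes is the 15-minute stop tolerance plus the connection and priming delay. The delay has no stated value, so 20 - 15 = 5 minutes is implied.

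**Direction under each reference duration**

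| Reference | Control (drained at 5 h) | Device (up to 5 h 20 min) | Effect on device minus control |
|---|---|---|---|
| 5 h 20 min in both arms | stopped early; UF equal to or higher than at 5 h 20 min | on target | equal or lower: favours control, as 6.2.6 says |
| 5 h in both arms (5.1.1, 5.2, 6.2.7.1) | on target | overruns with UF maintained | higher: favours device |

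**Inputs.** Pilot device UF per 5-hour treatment was 646 ml at 11 g/h and 739 ml at 14 g/h, and pilot control UF over 4 hours was 162 ml (section 3.8). The margin is 250 ml, the expected difference 574 ml, the conservative SD 330 ml, n = 19 and one-sided alpha 0.025 (section 7.1.1).

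Assumptions: a constant UF rate within a session, and a mean excess of 12.5 minutes (5 minutes of delay plus half of the 15-minute tolerance).

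**Size at pilot rates:** extra UF = UF / 300 min × extra minutes.

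- 20 min: 646/300 × 20 = 43.1 ml; 739/300 × 20 = 49.3 ml.
- 12.5 min: 646/300 × 12.5 = 26.9 ml; 739/300 × 12.5 = 30.8 ml.
- At 20 min this is 7.5-8.6% of 574 ml (43.1/574; 49.3/574).
- If the pilot sessions themselves lasted 5 h 20 min: 646/320 × 20 = 40.4 ml; 739/320 × 20 = 46.2 ml.
- The trial's 15 g/h dose was not in the pilot. Linear interpolation between 14 g/h (739 ml) and 20 g/h (863 ml), an assumption, gives 739 + (863 - 739)/6 = 759.7 ml. At 20 min that is 759.7/300 × 20 = 50.6 ml.

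**Size at the margin.** If the true 5-hour difference is exactly 250 ml, device UF is 250 ml plus control UF. With control UF of 162 ml (assumed from the 4-hour pilot dwell) it is 412 ml, or 82.4 ml/h. The error rate below is the upper tail of a noncentral t with 18 degrees of freedom, critical value 2.101 and noncentrality shift × √19 / 330.

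| Control UF (assumed) | Device UF | Shift at 12.5 min | Shift at 20 min | One-sided error |
|---|---|---|---|---|
| 0 ml | 250 ml | 10.4 ml | 16.7 ml | 3.4% to 4.0% |
| 162 ml | 412 ml | 17.2 ml | 27.5 ml | 4.05% to 5.3% |
| 300 ml | 550 ml | 22.9 ml | 36.7 ml | 4.7% to 6.7% |

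The nominal error is 2.5%. The 20-minute column assumes that every device session overruns by the full amount.

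**The case against.** The best defence is that 6.2.6 gives its reason openly and that the reason is sound at matched duration: extending the control to the device's time would not raise control UF. The protocol also does not use 5 hours as exactly 300 minutes. Section 7.1.4 accepts 5 ± 0.75 hours in both arms, so a session of 5 h 20 min is a per-protocol treatment. This stands in part. The sentence is true for one reference duration and incomplete as written. A reader might infer that the direction is simply reversed in every frame; the text does not support that. But the window tolerates deviations either way in both arms, whereas this overrun is foreseen, systematic and confined to the device arm. Nowhere is 5 h 20 min named as the target.

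A second stronger reading is that the bias is typically 43-49 ml and therefore 17-20% of the margin. That does not hold. The figure belongs to the stated maximum overrun, and it pairs UF rates seen far from the margin with the margin itself. With device UF of 646-739 ml, a difference of 250 ml would need control UF of 396-489 ml (646 - 250; 739 - 250), against 162 ml in the pilot. The figures that apply near the margin are the smaller ones, centrally 17-27 ml.

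Third, the constant rate is least certain in exactly these minutes. During connection and priming only the 1.36% fill acts, and the protocol does not say whether dosing continues through the stop tolerance. This stands as a limit on the size; it leaves the expected direction unchanged while device UF is positive.

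Finally, the overrun is disclosed, the times are recorded, and supporting analyses commonly sit in a statistical analysis plan that is not shown. The absence of such an analysis is therefore no fault. The point is the stated direction.

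**Conclusion.** The reassurance in 6.2.6 does not hold for the trial's own 5-hour objective, hypothesis and endpoint. Against those, the longer device time is expected to favour the device. It favours the control only if both arms are compared at about 5 h 20 min.

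The effect is modest. At pilot rates it reaches about 43-49 ml if the full 20 minutes is used, and is about 27-31 ml at an assumed mean excess of 12.5 minutes. At a true difference of 250 ml it is about 17-27 ml (10-37 ml for control UF of 0-300 ml), and the one-sided error is about 4-5% (3.4-6.7%) instead of 2.5%, with n = 19 and SD 330 ml. All of this assumes a constant UF rate. A result near the expected 574 ml would not be affected in substance; one close to 250 ml could be. The statement is worth correcting because it concerns the primary endpoint and errs in the direction of the claim.

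**What to change.** - **Section 6.2.6:** replace the sentence on direction with a statement that it depends on the reference duration and that, against the 5-hour endpoint, the overrun is expected to favour the device.
- **Section 6.2.5:** say that the equal duration of the two treatments is nominal.
- **Primary test:** leave it unchanged.
- **Reporting:** give recorded treatment time by arm.
- **Sensitivity analysis:** add one estimate of the paired UF difference that handles long and short device sessions alike. Scale device UF to 5 hours in both directions at the session's mean rate: UF × 5 / recorded hours. As a check, 646 + 43.1 = 689.1 ml over 5 h 20 min returns 689.1 × 300/320 = 646 ml. Keep control UF as recorded in the main version, and show a second version limited to control dwells near 5 hours. Present each as an estimate with its 95% confidence interval beside the 250 ml margin, not as a second pass/fail test.

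The cost is one corrected sentence, one qualifying word and one supporting analysis. No new data are needed, since Table 7 already has the end of fill and start of drain recorded and treatment time calculated. The downsides are that the supporting estimate may be slightly less favourable, that the restricted version may lose some sessions, and that constant-rate scaling is approximate.

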## 6.2.7 Endpoints

### 6.2.7.1 Primary endpoint

The primary endpoint has been defined to address the primary objective; to demonstrate that Carry Life® treatment at home results in an increased UF volume compared to a 2.27% glucose CAPD dwell.

Primary endpoint:

UF volume during 5-hour treatments at home (Carry Life® UF treatment vs. a 2.27% glucose CAPD dwell).

Rationale for the primary endpoint:

Carry Life® UF has been developed to address inadequate fluid management in PD patients which has been associated with increased morbidity, mortality, and technique failure.

### 6.2.7.2 Secondary endpoints

- AE and SAE rates.
- Peritoneal sodium removal.
- Glucose UF efficiency.
- Peak dialysate glucose concentration.

Rationale for the secondary endpoints:

- The Carry Life® UF system should be as safe to use as standard PD methods.
- Higher peritoneal sodium removal has been associated with increased survival.
- Glucose absorption in PD is associated with metabolic syndrome and increased body weight. An increased glucose efficiency means that a required UF volume may be achieved with a reduced glucose uptake.

- Hypertonic PD solutions are associated with peritoneal membrane deterioration which reduces the UF capacity resulting on technique failure. A higher dialysate glucose concentration also leads to a higher glucose uptake rate. Carry Life® UF is expected to obtain a higher UF volume with a lower dialysate peak glucose concentration.

#### 6.2.8 Methods and timing for assessing, recording, and analyzing of variables

The following clinical tests/assessments will be performed to assess the performance of the Carry Life® UF system (Table 7). The timing of the assessments in relation to the study visits is contained in Table 1.

**Table 7. The tests methods, recording and analysis of variables**

Test/assessment	Required measurements	Recording	Analysis	Source data
PD fill volume	Weight of full PD bags with or without outer wraps. Weight of plastic material (may be predetermined).	In-clinic visits, PET, and Carry Life® UF treatments: Home phase efficacy evaluations treatments (control and Carry Life® UF).	Calculated by electronic data capture (EDC): The weight of full PD bags minus weight of the plastic material.	Work sheets for measured data and eCRF for calculated data.
Drained volume	Weight of drain bags. Weight of plastic material (may be predetermined)	All CAPD dwells and Carry Life® UF treatments during home phase.	Calculated by EDC: The sum of all volumes drained for each treatment, including all dialysate sample volumes.  The drained volume in each drain bag is calculated as the weight of the drain bag minus the weight of the plastic material.	Work sheets for measured data and eCRF for calculated data.
Treatment time (hours)	Time for end of peritoneal fill and start of peritoneal drain.		Calculated by EDC: Time between "end of peritoneal fill" and "start of peritoneal drain"	Work sheets for measured data and eCRF for calculated data.
Glucose volumeexact	Weight of full glucose bag with or without outer wrap. Weight of used glucose bag. Weight of plastic material (may be predetermined)	Carry Life® UF in-clinic treatments and Carry Life® UF efficacy evaluation treatments (ml).	Calculated by EDC; Weight of full glucose bag minus weight of used glucose bag (g) divided by the density of the 50% glucose solution (1.2235 g/ml).	Work sheets for measured data and eCRF for calculated data.
Glucose volumeapprox for Carry Life® UF home treatments other than efficacy evaluation days (ml)	None, nominal volume for the 5 hour Carry Life® UF treatment at each dose 110 ml (11 g/h) and 150 ml (15 g/h) is used.	Daily during Carry Life® UF arm	N/A	eCRF (prescribed Carry Life UF glucose dose).

Test/assessment	Required measurements	Recording	Analysis	Source data
UF volumeexact (ml)	PD fill volume. Glucose volume. Drained volume.	In-clinic visits, Home phase efficacy evaluations treatments	Calculated by EDC; Drained volume-PD fill volume - Glucose volume exact .	Work sheets for measured data and eCRF for calculated data.
UF volumeapprox. (ml)	PD fill volume. Glucose volume. Drained volume.	All dwells/Carry Life® UF treatments during home phase.	Calculated by EDC; Drained volume-PD fill volume - Glucose volume approx.	Work sheets/electronic patient-reported outcome measures (ePROM) for measured data and eCRF for calculated data.
UF rate (ml/kg body weight/treatment)	UF volume exact . Body weight before treatment.	In-clinic phase, Carry Life® UF treatments.	Calculated by EDC; UF volume exact /Body weight before treatment.	Work sheets for measured data and eCRF for calculated data.
UF volume % increase	UF volume exact	End of In-clinic phase	Calculated by EDC; ([UF volume exact Visit4/ UF volume exact Visit3]-1)*100	eCRF
Dose determination	UF volume % increase	End of In-clinic phase	Determined by EDC according to dose determination algorithm.	
Dialysate glucose concentration	Glucose concentration in drain samples	In-clinic phase, PET, and Carry Life® UF treatments: PET: T0, T1h, T2h, T4h Carry Life UF: T0, T1h, T2h, T3h, T4h, T5h, peritoneal drain	Laboratory analysis	Laboratory data
Peak dialysate glucose concentration	Glucose concentration in drain samples	In-clinic phase, Carry Life® UF treatments: T1h, T2h, T3h, T4h, T5h	Data analysis	N/A
PET	Sodium and creatinine concentration in dialysate.	PET, at T0, T1 and T2 T4	D/P creatinine  Transfer type determined as D/P creatinine at 4h Low: 0.34-0.50 Low average: 0.50-0.65 High average: 0.65-0.81 High: 0.81-1.03  Sodium dip: Dialysate sodium: T1 minus T0	Laboratory data

Test/assessment	Required measurements	Recording	Analysis	Source data
Glucose absorption	PD fill volume. Glucose volume exact . Drain volumes (peritoneal drain + Carry life UF drain bag). Glucose concentration of drain volumes (peritoneal drain + Carry life UF drain bag).	In-clinic (Carry Life UF treatments) Home phase efficacy evaluations treatments (control and Carry Life® UF).	Sum of glucose added (PD fill volume (ml) * glucose concentration of PD solution (13.6 or 22.6 g/ml) + Glucose volume exact (ml) * 0.5 g/ml) minus the sum of glucose drained (peritoneal drain volumes * the glucose concentration of drain volumes (g/ml)).	Work sheets for measured data, laboratory data and eCRF for calculated data.
Fluid intake and urine output.	Fluid intake volume and urine volume.	During the PET and Carry Life® UF study session.	For evaluation.	Worksheets
Body surface area (BSA)(m^2)	Subject height and body weight.	V2 before treatment	(BSA according to Gehan and George = $0.0235 \text{Body weight (kg)}^{0.514} \text{Height (cm)}^{0.42246}$ ).	Worksheets for measured data and eCRF for calculated data
Urine clearance	24-h urine volume and 24-h urine sample for analysis of creatinine and urea.	Urine collection completed prior to V2, V5 and V6.	Calculated by EDC; Calculation of creatinine and urea clearance and residual renal function normalized to 1.73m  BSA.  Urinary clearance (ml/min) of creatinine and urea is calculated using the following equation: $Cl = \frac{(U_s \cdot V_u)}{(P_s \cdot T)} * 1.73 / BSA$ where U s is the concentration of the substance in the 24-hour urine sample, V u urine volume (ml), P s is the concentration in plasma of the substance, and T total time for urine collection (min).	Worksheets and laboratory data
Residual renal function	Urine clearance of creatinine and urea	N/A	Calculated by EDC; (Cl creatinine +Cl urea )/2	Worksheets and laboratory data, eCRF for calculated data. Laboratory data
Body weight change	Body weight.	Before and after the PD exchange in PET and Carry Life® UF study sessions and daily during the home phase	Body weight after minus body weight before.	Worksheet or eCRF (in case of electronic diary use during home phase)

Test/assessment	Required measurements	Recording	Analysis	Source data
Peritoneal creatinine and urea removal	Carry Life UF drain volume. Peritoneal drain volume. Concentrations of creatinine and urea in drain volumes.	In-clinic Carry Life® UF study sessions. Efficacy evaluation treatments during home phase.	Data analysis. The sum of removal in Carry Life® UF drain volume and the peritoneal drain.	Work sheets and Laboratory data
Blood chemistry: Na + , K + , Mg 2+ , ionized Ca 2+ , PO 4  , albumin, creatinine, urea and PTH	Concentration of solutes in blood samples.	At study start (before PET visit 2, and at end of each arm (V5 and V6).	Laboratory analysis.	Laboratory data.
Peritoneal solute removal Na + , K + , Ca 2+ , PO 4  , albumin, creatinine and urea	PD fill volume. Concentration of each solute in the PD solution (known) Drain volumes (peritoneal drain + Carry life UF drain). Concentration of each solute in drain volumes (peritoneal drain + Carry life UF drain bag).	In-clinic, Carry Life UF treatments (V3 and V4) and during efficacy evaluation days during home phase	Data analysis. The difference between amount added in the PD solution (volume * concentration) and the sum of the amounts removed in drained fluid (volumes * concentrations)	Work sheets for measured data and eCRF for calculated data. Laboratory data
Vital signs	Blood pressure and heart rate (HR).	During visits to the clinic (before and after treatment). Blood pressure and heart rate daily by patient during home phase.	Monitoring of status and changes.	Worksheet or eCRF (in case of electronic diary use during home phase).

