Carry Life® UF treatments: 10 ml dialysate samples at 0, 1, 2, 3, 4 and 5 hours will be analyzed for dialysate glucose and sodium for evaluation of dialysate glucose and sodium concentrations during treatment. All PD fluid automatically drained (and any additional drains) during the Carry Life® UF treatment will be pooled. The pooled PD fluid, plus the final peritoneal drain will be analyzed for dialysate glucose, sodium, potassium, calcium, phosphate, albumin, creatinine, and urea for calculation of glucose ultrafiltration (UF) efficiency, glucose absorption and peritoneal removal of the listed substances.

**Home phase efficacy evaluation days, during week 2 and week 4 or each arm:** Drained dialysate from the control and Carry Life® UF efficacy evaluation treatments (Carry Life® UF drain bag + final peritoneal drain) will be collected by a research assistant for analysis of dialysate glucose, sodium, potassium, calcium, phosphate, albumin, creatinine, and urea, for calculation of glucose absorption, glucose UF efficiency, and peritoneal removal of the listed substances.

j. **In-clinic phase:** The volume and glucose concentration of PD bags used for the PET and Carry Life® UF treatments will be recorded.

**Home treatment phase:** The subjects will record information of all PD bags used (volume and glucose concentration for glucose-based solutions and volume for icodextrin).

k. **In-clinic phase:** The PD bag and glucose bag will be weighed by a clinical professional before the treatment and the drain bag(s) will be weighed after the treatments for calculations of fill volume, drained volume and UF volume.

**Home treatment phase:** Subject will record fill and drain weights of all dwells every day during the home phase.

**Home treatment phase efficacy evaluation days:** A research assistant will weigh the solution bags (PD bag and glucose bag), and the drain bags for calculations of fill volume, drained volume and UF volume.

l. 24-hour urine volume and urine concentration of creatinine and urea will be collected for calculation of residual renal function.

m. The patient will weigh the PD bag, glucose bag and drain bag(s) for each CAPD dwell/Carry Life® UF treatment during the home phase of the study for evaluation of weekly UF volume.

n. To assess the Carry Life® UF safety at the different glucose doses, each in-clinic Carry Life® UF treatment will be evaluated for the following:

1) a systolic blood pressure of < 100 mmHg.

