During the home treatment phase subjects will record clinical measurements and solution weights daily. Primarily, the subjects will enter the data (e.g., weight and blood pressure) into a mobile application. The data entered into the App will be transferred directly into the eCRF and there is no additional source documentation expected and thus these values are not subject to source data verification through the monitor. In case a subject does not use the App, but records data in a paper-based diary instead, the data are entered by dedicated site staff into eCRF and are subject for source data verification. However, in case of out of limit measurements the site is going to be alerted by means of a query and is going to follow-up with the patient to verify and discuss the entered data for any potential error. When copies of original source documents as well as printouts of original electronic source documents are retained, these shall be signed and dated by a member of the investigation site team with a statement that it is a true reproduction of the original source document. Copies of the source data shall remain at the clinical investigation site when the investigation is completed allowing an independent account of the investigation process.

The data from the eCRF will be managed in an EDC system. The EDC database will be programmed to use the input data from the eCRF to calculate output data including the endpoint measures (e.g., UF volume, peritoneal removal of the substances analyzed in the dialysate, and glucose efficiency). To be able to perform the calculation the following constants will be used:

- Glucose molecular weight: 180.16 g/mol.
- 50% glucose solution concentration: 0.5 g/ml.
- Density 50% glucose solution: 1.2235 g/ml.

Additionally plastic weights of solution bags and drain bags may be pre-weighed and used to calculate fill and drain volumes.

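### Table 7 allows the full glucose bag to be weighed in its outer wrap, but the printed glucose-volume formula has no term to remove the wrap

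*Protocol*

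**What the plan says.** In Protocol section 6.2.8, Table 7, the row for the exact glucose volume lists these measurements: "Weight of full glucose bag with or without outer wrap. Weight of used glucose bag. Weight of plastic material (may be predetermined"). The calculation assigned to the EDC in the same row is: "Weight of full glucose bag minus weight of used glucose bag (g) divided by the density of the 50% glucose solution (1.2235 g/ml").

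The PD fill row offers the same choice about the wrap, but its calculation is "The weight of full PD bags minus weight of the plastic material". The drained-volume row also subtracts plastic.

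The glucose volume then enters UF volume as "Drained volume-PD fill volume - Glucose volume". Table 7 uses that UF volume for the UF rate and for the percentage increase behind dose determination. On the efficacy evaluation days it is the primary endpoint. The glucose volume also enters glucose absorption, the denominator of glucose UF efficiency.

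Section 8.1 fixes the constants: "Density 50% glucose solution: 1.2235 g/ml" and "50% glucose solution concentration: 0.5 g/ml". It mentions pre-weighed plastic for fill and drain volumes and does not name the glucose volume.

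**The concern.** Subtracting the used bag from the full bag cancels the bag's own plastic, because it is on the scale both times. A wrap that is present only at the first weighing does not cancel. The formula would count it as glucose solution delivered to the patient. Once the plastic of the bag has cancelled, the only evident use for the listed plastic weight is to correct for a wrap, and the printed formula makes no such correction.

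Control dwells have no glucose bag, so the error would not cancel in the paired difference. In glucose UF efficiency it acts twice in the same direction, lowering the numerator and raising the denominator. In dose determination it could move the ratio of Visit 4 to Visit 3 UF either way if the two bags were weighed in different states.

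**Working it through.** **The plan's own figure first.** Table 7 gives nominal glucose volumes: "110 ml (11 g/h) and 150 ml (15 g/h) is used". Dose × 5 h ÷ 0.5 g/ml gives 11 × 5 / 0.5 = 110 ml and 15 × 5 / 0.5 = 150 ml, so both are reproduced. The glucose infused at 11 g/h is 55 g.

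**Error for a wrap of W g**, on at the first weighing and off at the second:
- volume overstated, and UF understated, by W / 1.2235 ml;
- glucose added, and so glucose absorbed, overstated by 0.5 × W / 1.2235 = 0.409W g.

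The wrap weight is an assumption; 5, 10 and 20 g are shown.

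| W (g) | UF understated (ml) | Share of 250 ml margin | Glucose absorbed overstated (g) | Share of 55 g |
|---|---|---|---|---|
| 5 | 4.1 | 1.6% | 2.0 | 3.7% |
| 10 | 8.2 | 3.3% | 4.1 | 7.4% |
| 20 | 16.3 | 6.5% | 8.2 | 14.9% |

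**Glucose UF efficiency.** Inputs are the Tmed-007 means in section 3.8: 646 ml and 17.0 ml/g at 11 g/h; 739 ml and 14.5 ml/g at 14 g/h. Absorbed glucose is approximated as mean UF ÷ mean efficiency: 646 / 17.0 = 38.0 g and 739 / 14.5 = 51.0 g. The distorted efficiency is (UF − W/1.2235) / (absorbed + 0.409W).

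| W (g) | 11 g/h (ml/g) | Change | 14 g/h (ml/g) | Change |
|---|---|---|---|---|
| 5 | 16.0 | −5.7% | 13.9 | −4.4% |
| 10 | 15.2 | −10.9% | 13.3 | −8.4% |
| 20 | 13.6 | −19.8% | 12.2 | −15.7% |

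**UF percentage increase.** Section 6.2.2 gives an example of 500 ml at Visit 3 and 620 ml at Visit 4: 620/500 − 1 = 24%.
- Wrap on at Visit 3 only, 620 / (500 − W/1.2235) − 1: 25.02%, 26.1% and 28.2% for 5, 10 and 20 g.
- Wrap on at Visit 4 only, (620 − W/1.2235) / 500 − 1: 23.2%, 22.4% and 20.7%.
- Wrap on at both, (620 − W/1.2235) / (500 − W/1.2235) − 1: 24.2%, 24.4% and 24.8%.

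Of these, only a wrap at Visit 3 alone takes this example past 25%.

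**Added noise in UF.** If half the subjects were affected by a 20 g wrap, the added SD would be 16.3 / 2 = 8.2 ml. Against the planning SD of 236 ml, √(236² + 8.2²) = 236.1 ml, which is negligible.

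**The case against.** The strongest reply is that Table 7 permits a practice that could cause an error but does not show that one occurs. Nothing in the protocol text says what is on the scale at the second weighing. Section 6.4.3 refers to detailed written weighing procedures; Attachments E and F are those procedures, and their text is not shown. Listing a plastic weight may mean that a correction is intended and the formula is shorthand. This stands as a limit: the error is conditional. It does not clear the row, because the EDC is to compute the endpoint measures and the printed formula has no such correction.

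Three stronger readings are tempting and should not be drawn.

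- A reader might infer that patients' weighing habits at home contaminate the primary endpoint. They do not. The exact volume is used only for in-clinic and efficacy evaluation treatments, which are weighed by clinical staff, a research assistant or a sponsor representative. Patients' own weighings feed the approximate UF volume, which uses the nominal 110 or 150 ml.
- A reader might infer that the used-bag weight is missing from the plan, because footnote k of Table 1 says for the in-clinic phase that the "glucose bag will be weighed by a clinical professional before the treatment and the drain bag(s) will be weighed after the treatments". Table 7 expressly requires the used-bag weight, and the efficacy-day wording of footnote k is not limited to the time before treatment. Only the in-clinic wording, there and in section 6.4.1 item 8, is incomplete.
- A reader might infer that dose assignment is generally unreliable. With the same practice at both visits, the protocol's own example stays below 25% over the whole assumed range.

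**Conclusion.** The mismatch within the Table 7 row is certain; its effect is conditional on weighing practice. It arises only if the full bag is weighed wrapped, the used bag is weighed unwrapped, and nothing outside the printed formula corrects for it.

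For the primary endpoint it is minor: 4 to 16 ml for an assumed 5 to 20 g wrap, at most 6.5% of the margin. The direction is against the device. A reader might suspect that the error could produce a false claim of superiority; it cannot, because it only lowers device-arm UF and leaves the control dwell untouched.

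The more material effect is on glucose UF efficiency, roughly 6 to 20% too low at 11 g/h pilot values. That matters for the estimate more than for the test: even 13.6 ml/g is over twice the pilot control value of 5.9 ml/g. A UF increase close to 25% could be moved across the criterion if the two in-clinic bags were weighed in different states.

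All sizes rest on the assumed wrap weight, and the efficiency figures also on a ratio of pilot means as a rough stand-in for absorbed glucose.

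**What to change.** In Table 7, remove the wrap option from the glucose row and require the full and the used bag both to be weighed without the wrap; the existing formula is then correct. Alternatively keep the option, record whether the wrap was on, and program the EDC as (full bag − wrap weight if wrapped − used bag) / 1.2235. Align the weighing worksheets, Attachments E and F, and the statement on plastic weights in section 8.1.

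As a minor clarification, have the in-clinic wording of footnote k and section 6.4.1 item 8 name the weighing of the used glucose bag after treatment, which Table 7 already requires.

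The cost is one table row, at most one EDC formula, and a line in the worksheets. No new procedure is needed, since Table 7 already lists a plastic weight and both bag weights.
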